4.6. Follow-up of participants

All participants of arm 3 who took the self-sample and tested positive will be contacted by phone 2-3 weeks after their participation to inform them on their test result.

All participants (arm 2 and 3) will be contacted by phone **3 months** after their participation:

- to gauge the **knowledge** on cervical cancer screening after the education session
- to verify whether they got a **pap smear** (all women in arm 2 and HPV-positive women of arm 3)
 - if not, why not
 - was an appointment made?
 - if not, why not

In case women do not have a phone, the community-based researcher can discuss with them the best way to schedule a day or set a temporary 'drop-in centre' for them to come in.

5. Data collection

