A community-based researcher will educate women about sexual health and cervical cancer by using the materials that will be developed by the ELEVATE team. In addition, women will receive information about self-sampling and will be instructed by the community-based researcher on how to take a self-sample using an illustrative cartoon. Women will then be asked to take a sample on-site. The researcher will collect all samples and bring them to the laboratory of UZ Ghent for analysis by an HPV test (yet to be decided which one). Sample analysis is expected to take 2 weeks time. Women who tested positive for HPV will receive a follow-up phone call to notify their result and will again be informed about cervical cancer screening (pap smear) and about where they can obtain these services; they will receive a contact number to make an appointment as well as information on how to reach the place of the consultation.

Outcome measures that will be examined for arm 3 are:

- Participation rate (i.e., women invited/women who attend the session)
- Knowledge, willingness and uptake of cervical cancer screening prior to the session
- Acceptability of self-sampling
- Uptake of the self-sampling test (women who attend the session/women who take the self-sample)
- Attitudes towards self-sampling (reasons to accept/decline the self-sample; advantages and disadvantages versus conventional screening)
- User experiences among those who took a self-sample (easy/difficult; painless/painful; trustworthy/untrustworthy; etc.)
- Uptake of cervical cancer screening through standard services:
 - A 3-month follow up is proposed to check whether the woman made/went to the appointment
- Knowledge of as well as willingness to get screened for cervical cancer screening will also be assessed during the 3 month follow-up phone call
- Feasibility and cost of the intervention

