3.2. Specific objectives

Objective 1: Assess and compare **attendance rates** following invitation to participate to the study

Hypothesis 1.1: Attendance will be higher when women are offered self-sampling compared to when women are only offered an educational session.

Objective 2: Evaluate the current **knowledge, willingness and uptake** of cervical cancer screening among participants of the acceptability study (arm 2 & 3); assess knowledge improvement and willingness to get screened 3 months after the intervention

Hypothesis 2.1: Knowledge and willingness to get screened will be poor and uptake of cervical cancer screening among the participants will be lower than the national average (but similar to results found in arm 1)

Hypothesis 2.2: After the information sessions, women will be able to link cervical cancer with HPV and will understand the benefit of screening; willingness to be screened will have increased

Objective 3: Assess **attitudes towards and users' experiences** of the HPV self-sampling test among hard-to-reach women (i.e. participants in arm 3)

Hypothesis 3.1: Attitudes towards on-site HPV self-sampling will be overall positive

Hypothesis 3.2: Women who use the self-sampling tool will have positive users' experiences related to the self-sampling device.

Objective 4: Compare the uptake of the on-site HPV testing (arm3) with the current national screening services (arm1) and with off-site referrals (arm2)

Hypothesis 4.1: Uptake of on-site HPV self-sampling will result in an increase in screening coverage compared to standard practices. (arm 3 vs arm 1)

Hypothesis 4.2: On-site HPV self-sampling will have higher uptake than referrals to off-site screening. (arm 3 vs arm 2)

Hypothesis 4.3: Referral to off-site screening following participation in an educational session on cervical cancer will result in higher screening coverage compared to current practices. (arm 2 vs arm 1)

Hypothesis 4.4: Uptake of off-site screening among those who refuse the self-sampling in arm 3 will be lower than uptake of off-site screening in arm 2

Objective 5: Examine the impact of HPV self-sampling on follow-up testing and care

Hypothesis 5.1: Women whose on-site HPV testing came out positive will go for follow-up testing and care

Objective 6: Assess the **feasibility** of the information session and the self-sampling test

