5.2.2. Questionnaires

5.2.2.1. *Self-administered questionnaire: knowledge, willingness and uptake of conventional screening (arm 2 and arm 3)*

A self-administered questionnaire will be applied to all participants at the start of each session to assess their current knowledge, willingness to get screened (conventionally) and uptake (*Obj 2*). Through this questionnaire, also socio-demographics, sexual behaviour and pregnancy history will be collected, as well as barriers of accessing cervical cancer screening.

Knowledge will be assessed through verifying whether the participant 1) has heard of cervical cancer, 2) knows the human papillomavirus (HPV) as primary cause, and 3) knows HPV is an STI.

Uptake of conventional screening will be assessed by asking participants' screening history, including 1) lifetime screening, 2) age at first screening and number of pap smears received, and 3) being screened in the last 3 years.

Participants will be asked to indicate their willingness to receive a pap smear and reasons for opting/not opting for conventional screening (reasons for interest/disinterest in continuation among those with previous pap smear uptake). Participants will also be asked to indicate acceptance of self-sampling. (See Appendix I: questionnaire 1)

5.2.2.2. *Self-administered questionnaire: attitudes towards self-sampling (arm 3)*

A self-administered questionnaire will be applied to all participants in arm 3 after the educational session, and before self-sample taking, to assess attitudes regarding self-sampling (pre-intervention) (*Obj 3*).

Attitudes will be assessed through asking participants to use 5-point Likert scale responses to indicate their perceptions of self-sampling and reasons for accepting or not-accepting the self-sample device. (See Appendix II: questionnaire 2)

5.2.2.3. *Self-administered questionnaire: users' perspectives in self-sampling (arm 3)*

A self-administered questionnaire will be applied to all participants in arm 3 who took a self-sample to assess users' experience regarding self-sampling (post-intervention) (*Obj 3*).

Users' perspectives will be assessed through asking participants to use 5-point Likert scale responses report their experience with the self-sampling brush. (See Appendix III: questionnaire 3)

5.2.2.4. *Follow-up questionnaire: knowledge, willingness and uptake of conventional screening (arm 2 and arm 3)*

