A questionnaire will be applied during a follow-up phone call 3 months after the session to assess whether or not a screening appointment was made and participants got screened (=uptake), as well as to evaluate

knowledge after receiving the informative session (*Obj 2, Obj 4 and Obj 5*). (See Appendix IV: questionnaire 4)

Knowledge and willingness to get screened will be assessed by applying short, closed questions in order to quickly evaluate these outcomes by phone.

Women will be contacted through a message, phone call or e-mail (according to their preference) asking them when would be convenient for them to answer some questions. Women will be contacted up to 5 times maximum before considering them lost-to-follow.

Each participant will be attributed a unique identifier alpha-numeric code that will be used to link the respective questionnaires and to ensure pseudonymization of the data. The information that links the unique identifier code to the name and contacts of the participants will be registered. Only the community-based researcher (healthcare professional or community health worker) responsible for the data collection will have access to these personal data. No other member of the research team will have access to the name and contacts of the participants.

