6.1. Quantitative data

The primary endpoint is the participation in screening which is defined in Arm 1 as the proportion of women who had a PAP smear taken by a GP or gynaecologist within the national screening program, in Arm 2 as the proportion of women who go for PAP smear after attending the information session with targeted referrals for off-site screening and in Arm 3 as the proportion of women who accept to take an HPV self-test on site after the information session.

Two important measures of take-up will be estimated:

Take-up 1 - To compare the take-up of an on-site HPV screening intervention with the current national screening services accounting for self-selection of women who decide to attend clinics (arm 1 vs. arm 3).

Take-up 2 - To compare the take-up of an on-site HPV screening intervention with targeted referrals to off-site screening (population impact regardless of self-selection) (arm 2 vs. arm 3).

Sample calculation was defined according to an estimated increase in take-up compared with current screening coverage for each study country.

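### Sections 4.6 and 5.2.2.4 disagree on which arm 3 women are asked about Pap-smear uptake at 3 months; if 4.6 is followed, Hypothesis 4.4 has no arm 3 data

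*Protocol*

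**What the plan says.** Section 4.6 sets out the 3-month contact: "All participants (arm 2 and 3) will be contacted by phone". Two items follow. The knowledge item carries no restriction. The Pap-smear item, with its sub-items on appointments and reasons for not going, is restricted to "all women in arm 2 and HPV-positive women of arm 3".

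Section 5.2.2.4 describes the questionnaire used in that call. Its heading reads "Follow-up questionnaire: knowledge, willingness and uptake of conventional screening (arm 2 and arm 3"), and its text says the call establishes "whether or not a screening appointment was made and participants got screened (=uptake"). It names no subgroup and assigns the questionnaire to Objectives 2, 4 and 5.

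The arm 3 outcome list in section 3.1 includes uptake of screening through standard services and says "A 3-month follow up is proposed to check whether the woman made/went to the appointment", also without mention of the HPV result.

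Hypothesis 4.4, under Objective 4 in section 3.2, predicts that "Uptake of off-site screening among those who refuse the self-sampling in arm 3" will be lower than off-site uptake in arm 2.

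**The concern.** Two sections define different respondents for the same questions in the same call, and the protocol does not say which prevails. The women on whom they differ include those Hypothesis 4.4 is about. If field teams work from section 4.6, decliners in arm 3 are phoned and asked about knowledge, but not whether they were screened elsewhere. An analysis plan cannot repair this later, because the answers would never have been collected. With teams in four countries, there is also room for different sites to follow different sections.

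**Working it through.** The protocol gives no sample size, refusal rate or HPV prevalence tied to this point, so the check is a comparison of texts and of who falls into which group.

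**Step 1: who is asked.** By self-sample outcome, arm 3 divides into three groups.

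| Arm 3 group | Asked under 4.6 | Asked under 5.2.2.4 | Needed for Hypothesis 4.4 |
|---|---|---|---|
| Self-sample taken, HPV-positive | yes | yes | no |
| Self-sample taken, HPV-negative | no | yes | no |
| No self-sample taken | no | yes | yes |

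Section 4.6 covers 1 of 3 groups. Section 5.2.2.4, read as written without a limit, covers 3 of 3. These are counts of groups, not shares of women.

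**Step 2: the overlap that matters.** HPV status in the study comes only from the self-sample. A decliner has no result and cannot be an HPV-positive arm 3 woman in the sense of section 4.6. The overlap between decliners and the arm 3 women asked under 4.6 is empty, so the arm 3 group for Hypothesis 4.4 is 0 women at any sample size and any refusal rate. Under 5.2.2.4 it is all decliners reached at 3 months.

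**Step 3: whether another source fills the gap.** The planned instruments are these:

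- Participation register (5.2.1): counts women invited and participating.
- Questionnaire 1 (5.2.2.1): completed at the start of the session; it records past screening, so it cannot show later uptake.
- Questionnaire 2 (5.2.2.2): attitudes, completed before sampling.
- Questionnaire 3 (5.2.2.3): experience, only among women who took the sample.
- Questionnaire 4 (5.2.2.4): the 3-month call itself.

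The list of data to be entered in section 7 adds nothing to these. No other source records off-site screening by decliners after the session.

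**Step 4: what else depends on the item.**

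- Primary endpoint: section 6.1 defines participation "in Arm 3 as the proportion of women who accept to take an HPV self-test on site after the information session", which does not use the 3-month call.
- Hypotheses 4.1 and 4.2 use on-site self-test uptake for arm 3; the arm 2 side of 4.2 comes from arm 2 women, all of whom are asked under either text.
- Hypothesis 4.3 compares arm 2 with arm 1.
- Hypothesis 5.1 needs HPV-positive women, who are asked under either text.

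Affected: 1 of the 4 hypotheses under Objective 4 (4.4 only), and 0 of the 2 take-up comparisons in section 6.1.

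**The case against.** The best reply is that the sections can be read together. Section 5.2.2.4 describes the questionnaire in general terms, and 4.6 specifies who gets one item; the heading of 5.2.2.4 stays true if only some arm 3 women answer the uptake questions. The descriptions of questionnaires 1 to 3 each say that all participants, or all in a named group, complete them, whereas 5.2.2.4 does not. The appointment in section 3.1 may mean only the referral of HPV-positive women. The link to Objective 4 could be satisfied by arm 2 data alone. Finally, questionnaire 4 is in Appendix IV, which is not in the text at hand, and its routing may settle the matter in practice.

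Part of this stands. The conflict is between an explicit restriction and an unrestricted statement, not between two explicit rules, and section 3.1 is weak support. That countries would diverge is a possibility, not something the text shows.

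The central point survives. If the harmonising reading is right and 4.6 governs, no decliner is asked and Hypothesis 4.4 cannot be examined; the reading that removes the conflict between sections confirms the conflict with the hypothesis. A suitable routing in Appendix IV would rescue the data but would still leave 4.6 wrong. Section 5.2.2 also states a subgroup where it intends one, as with the women who took a sample in 5.2.2.3, which favours reading 5.2.2.4 as unrestricted.

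**Conclusion.** The concern holds. Section 4.6 as written excludes the arm 3 women whom Hypothesis 4.4 requires, and it does not match section 5.2.2.4. Following 4.6 gives 0 arm 3 women for that comparison; following 5.2.2.4 gives every decliner reached. The first figure follows from the wording alone. The second assumes that the absence of a limit in 5.2.2.4 means none was intended. The 4.6 wording also leaves HPV-negative self-samplers out of the arm 3 outcome on standard-service uptake in section 3.1, if that outcome is meant for all arm 3 women.

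The consequence is narrow: one hypothesis is lost, while the primary endpoint and the other comparisons checked above stand. It should be fixed because the loss would be complete and could not be recovered afterwards.

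**What to change.** Change the parenthesis in section 4.6 so that the Pap-smear and appointment questions go to all women in arm 2 and arm 3, which brings it into line with section 5.2.2.4. If the sponsor prefers not to ask HPV-negative self-samplers, whose off-site uptake Hypothesis 4.4 does not need, the minimum is all women in arm 2 and, in arm 3, HPV-positive women plus women who took no self-sample; section 5.2.2.4 should then state the same limit. In either case, check that questionnaire 4 in Appendix IV is put to the same women.

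One related clarification: section 4.5.1 gives only notification of a positive result as the reason for collecting telephone numbers in arm 3. The protocol should say that decliners' contact details are also recorded, so that the call planned in 4.6 can reach them.

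The cost is one parenthesis, matching text elsewhere, and a few closed questions in a call these women already receive. Calls become slightly longer; no extra contact is needed.

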5.1. Arm1

We will contact the respective instances in each study country to ask if more detailed data are available on screening coverage of the target group of socio-economically vulnerable women.

Outcome measures that will be examined for arm 1 are:

- Screening coverage at national level
- Screening coverage in the respective research area in each study country
- Follow-up rate among women who test positive (i.e. have a positive pap smear)

5.2. Arm 2 and arm 3

5.2.1. Participation registers

Participation registers will be used during the pilot to keep track of the participation rate (*obj 1*).

$$\textit{Participation rate} = \frac{\textit{number of women who participate}}{\textit{number of women who were invited}}$$

The number of women who are invited will be defined by the number of leaflets (invitation letters handed out).

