- Have the willingness and the time to collaborate
- Extra asset: female

3) *People that are working or volunteering in the organizations* participating in the acceptability study. These will have a similar profile as the previous group, but additionally they are active in the organization and possibly have a professional relationship with the women. During the focus group discussions, it was reported that trust will be an important facilitator during the information sessions and to encourage women to take a self-sample. Therefore, we aim to invite a familiar face to the information sessions as much as possible. Due to the workload of the organizations, this might not always be possible. However, we will ask if they could express their assent about study participation to women visiting their organization and if possible promote the sessions in their specific working groups or group activities. In addition, we will ask for the organization's support to ensure that all sessions are adapted to the specific target group (culturally sensitive and comprehensible).

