4.3. Recruitment of participants

In agreement with the participating organizations, the research team (including the community-based researchers) will hand out invitations (leaflets) to invite women to informative sessions on cervical cancer screening. While handing the invitation, the researcher will shortly describe the goal of the session, emphasizing the benefits for the women. If women are invited for arm 3, they will also be told that they will be offered a self-screening test during the session. Women will receive a leaflet stating the time and place they are expected. Women will be asked to invite other women as well.

We aim to link the sessions to group activities where women are already gathered such as sport activities, integration programs and meals in social restaurants. Therefore, we will work closely with the social

workers and volunteers active in the organizations and will ask for their support to invite women. However, we expect that their contribution will be limited due to their day-to-day workload and tasks.

We will explore with the respective organizations what the best approach is in their context with regard to the timeframe between the invitation and the information session. We learned during the focus group discussions that for many socio-economically vulnerable women it is difficult to commit to show up on another day, for various reasons. Therefore, we aim to organize the educational sessions directly following their group activity, integration class or meal in the restaurant (i.e. the moment they will be invited). In some subgroups of women, such as young mothers, it seems advisable to inform them that they will need to stay a bit longer so they can organize this.

All participants will be offered a small incentive for study participation, such as a voucher.

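### The Objective 1 participation rate counts all participants over leaflets handed out, but women asked in by other women have no described leaflet or count, so the rate need not be a proportion

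*Protocol*

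**What the plan says.** Section 5.2.1 defines the participation rate for Objective 1 as the number of women who participate over the number who were invited. It then fixes the denominator: "The number of women who are invited will be defined by the number of leaflets (invitation letters handed out". The numerator is not limited to women who received a leaflet.

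Section 4.3 describes how women are invited:

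- By the research team: "the research team (including the community-based researchers) will hand out invitations (leaflets) to invite women to informative sessions on cervical cancer screening". The same paragraph says in general terms that women get a leaflet giving time and place.
- By other women, in the very next sentence: "Women will be asked to invite other women as well".
- With help from the organisations, where the team will work with social "workers and volunteers active in the organizations and will ask for their support to invite women". Section 4.2.2 also asks these people to "if possible promote the sessions in their specific working groups or group activities".

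Two statements bear on how large the additional routes may be. On the organisations' staff, section 4.3 says "we expect that their contribution will be limited due to their day-to-day workload and tasks". On timing it says "we aim to organize the educational sessions directly following their group activity".

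The content of the invitation differs by arm: "If women are invited for arm 3, they will also be told that they will be offered a self-screening test during the session". Hypothesis 1.1 in section 3.2 expects higher attendance in arm 3 than in arm 2.

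Section 3.1 prints the participation rate in both arms as invited over attended, and arm 3 self-sampling uptake as attended over sampled. These are the inverse of the formula in 5.2.1 and of the proportion described in 6.1.

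**The concern.** A participation rate is a proportion only if every woman in the numerator is also in the denominator. Here the denominator counts pieces of paper and the numerator counts women, and section 4.3 plans a route by which a woman may attend without having been given a counted piece of paper. The text neither says that women invited by peers receive a counted leaflet nor excludes it.

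At stake is the one outcome that answers Objective 1. If such women attend, each arm's rate contains attendees whose invitation was never counted. If they are relatively more frequent in one arm, part of the difference tested under Hypothesis 1.1 reflects how invitations were counted and not how often invited women came. As described, the register would not show afterwards whether the effect was negligible.

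**Working it through.** **Nothing to reproduce.** The protocol gives no expected participation rate, number of leaflets or sample size for Objective 1. All inputs below are assumed and only show how the definition behaves.

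**Inputs.** L = leaflets handed out; p = attendance among women given a leaflet; g = participants without a counted leaflet per leaflet-invited participant.

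**Recorded rate in one arm.** Leaflet-invited participants = pL and other participants = gpL, so

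R = (pL + gpL) / L = p(1 + g).

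| p | g = 0.05 | g = 0.10 | g = 0.25 |
|---|---|---|---|
| 0.30 | 31.5% | 33.0% | 37.5% |
| 0.60 | 63.0% | 66.0% | 75.0% |
| 0.90 | 94.5% | 99.0% | 112.5% |

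R exceeds 100% when g > 1/p − 1, which is 0.667 at p = 0.60 and 0.111 at p = 0.90. With g = 0 there is no error.

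**Opposite pull from ineligible invitees.** Eligibility is checked on the consent form (section 9.4), after the invitation. Suppose a fraction e of leaflets goes to women who cannot be included under section 4.2.1, and let p now be attendance among eligible leaflet recipients. Then R = p(1 − e)(1 + g). The two errors cancel when e = g/(1 + g): 0.10/1.10 = 0.091 for g = 0.10, and 0.25/1.25 = 0.20 for g = 0.25. A larger e makes the recorded rate too low. The protocol fixes neither e nor g, so the net direction is open.

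**Between arms, equal true attendance p, ineligible leaflets set aside.** Difference = p(g3 − g2); ratio = (1 + g3)/(1 + g2).

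- g2 = g3: difference 0, ratio 1.
- 0.05 (arm 2) v 0.10 (arm 3): 0.30 × 0.05 = 1.5 points or 0.60 × 0.05 = 3.0 points; ratio 1.10/1.05 = 1.048.
- 0.10 v 0.25: 0.30 × 0.15 = 4.5 points or 0.60 × 0.15 = 9.0 points; ratio 1.25/1.10 = 1.136.

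**A repair that would not work.** If a peer-invited woman is given a counted leaflet only on arrival, women invited this way who stay away are still missing from the denominator. The denominator becomes L(1 + pg) and R = p(1 + g)/(1 + pg). At p = 0.30 and g = 0.25 this is 0.375/1.075 = 34.9%, still above 30%.

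**The case against.** **Every invited woman may be meant to get a leaflet.** The general sentence about leaflets stands directly before the request to bring other women, and 5.2.1 equates invitations with leaflets. That reading is possible. However, the sentence sits in a description of the researcher handing out invitations and is not said to cover women invited by peers. If universal leaflets are intended, the protocol should say so.

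**Staff and volunteers.** A reader might infer that they invite outside the leaflet count. The documents do not support that: 5.2.1 does not limit who hands leaflets out, support in inviting is compatible with using the same leaflets, and the contribution is expected to be limited. This route is unclear and secondary; the peer route carries the point.

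**Small effect.** Sessions directly after the activity leave less room for peers to bring others. This is fair, and it also means that the 112.5% figure pairs high attendance with a value of g that may be unlikely in that very setting. It shows that the definition is unbounded; it is not a forecast.

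**Bias in favour of arm 3.** This is tempting to infer, because only arm 3 invitations mention the self-test. The protocol does not establish it. Moreover, if the offer leads women to bring others, the extra attendance is arguably an effect of the offer. Attendance per leaflet is then a usable measure of yield between randomly allocated organisations, but it answers a different question from how often invited women attend. That argues for reporting both.

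**Detail for a register template.** Field layout can be left there, but 5.2.1 itself fixes the denominator, so the mismatch is in the protocol.

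**Conclusion.** The mismatch is real and limited. As defined, the Objective 1 rate puts all participants over leaflets, while a planned invitation route has no described leaflet or count. The rate is therefore not guaranteed to be a proportion.

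It cannot be concluded that the reported rate will be too high. The peer route pushes it up by the factor 1 + g, and leaflets to ineligible women push it down. Nor can it be concluded that Hypothesis 1.1 is biased: through the peer route that requires g to differ between arms. Every figure above rests on assumed p, g and e.

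The effect is confined to Objective 1. The primary endpoint in section 6.1 does not use the leaflet count. The inverted ratios in section 3.1 are a separate, plain wording error; the formula in 5.2.1 makes the intent clear, and they add no weight to the leaflet point.

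**What to change.** 1. In the participation register, record for each attendee how she was invited: leaflet from the research team, staff or volunteer, or another woman. Base this on whether she was given a counted leaflet, not on whether she still holds it, since leaflets are lost or passed on.
2. Define the rate as leaflet-invited participants over leaflets handed out, by arm. Report all other attendees separately by arm and route, with total attendance per leaflet as a secondary measure of reach.
3. Alternatively, issue and count a leaflet for every peer invitation at the time it is made, not on arrival.
4. In section 3.1, print the ratios as attended/invited (arms 2 and 3) and sampled/attended (arm 3), to agree with 5.2.1 and 6.1.

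The cost is one or two register fields, a leaflet count, and possibly a lower reported rate. Invitation route cannot be reliably recovered later if it is not recorded at the session. Items 1 to 3 do not remove the effect of leaflets given to ineligible women, so the rate should still be described as attendance per leaflet and not as attendance among eligible women.
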